### **5 Study Objectives and Endpoints**

#### **5.1 Study Objectives**

Our goal for this study is to evaluate the feasibility, acceptability, and effect size of a previously developed online positive affect (PA) skills intervention—LARKSPUR (Lessons in Affect Regulation to Keep Stress and Pain UndeR control)—in a sample of patients with fibromyalgia syndrome (FMS).

##### **5.1.1 Objective**

**5.1.1.1** To maximize relevance and acceptability of content and delivery of LARKSPUR intervention among patients with FMS, a chronic pain population with known deficits in PA. This aim will establish the feasibility (recruitment and retention) and acceptability (helpfulness, satisfaction, and impact) of the multicomponent LARKSPUR intervention in patients with FMS.

**5.1.1.2** To conduct a randomized pilot trial to estimate the effect size of the LARKSPUR intervention in FMS pain (primary outcome), as well PA, depressive symptoms, physical functioning, and stress appraisals (secondary outcomes) and explore racial/ethnic disparities. We hypothesize that intervention participants will report more frequent PA, decreased depressive symptoms, enhanced physical functioning, improved stress appraisals,

and reduced FMS pain (intensity and interference) immediately following the intervention (approximately 8 weeks), and at 1-Month Follow-Up.

### **5.1.2 Hypotheses / Research Questions**

We hypothesize that the intervention will lead to more frequent daily PA, which, in addition to directly affecting depressive symptoms, will also have indirect effects through enhanced physical functioning and improved stress appraisals (*resilience mechanisms*). Decreased depressive symptoms, enhanced physical functioning, and improved stress appraisals, in turn, are hypothesized to lead to reduced FMS pain (*resilience outcomes*).

## **5.2 Endpoints**

### **5.2.1 Primary Endpoints**

**5.2.1.1** Recruitment as Measured by Rates of Enrollment

**5.2.1.2** Retention as Measured by Change in Enrollment

**5.2.1.3** Helpfulness, Satisfaction, and Impact as Assessed by Self-Report Participant Feedback Survey

**5.2.1.4** Length of Intervention Time as Measured by Number of Weeks to Complete Intervention

### **5.2.2 Secondary Endpoints**

**5.2.2.1** Change in FMS Pain as Measured by PROMIS Pain Intensity – Short Form 3a

**5.2.2.2** Change in FMS Pain as Measured by PROMIS Pain Interference – Short Form 6b

**5.2.2.3** Change in Depressive Symptoms as Measured by the Center for Epidemiologic Studies Depression Scale Revised (CESD-R-10)

**5.2.2.4** Change in Positive Affect as Measured by the Modified Differential Emotions Scale (mDES)

**5.2.2.5** Change in Positive Affect as Measured by the Positive and Negative Affect Scale (PANAS-GEN)

**5.2.2.6** Change in Physical Functioning as Measured by PROMIS Physical Functioning Short Form 10a

**5.2.2.7** Change in Physical Functioning as Measured by PROMIS Fatigue – Short Form 6a

**5.2.2.8** Change in Stress Appraisal as Measured by the Perceived Stress Scale

**5.2.2.9** Change in Affective Reactivity to Stress as Measured by the Daily Modified Differential Emotions Scale (mDES)

**5.2.2.10** Change in Affective Reactivity to Stress as Measured by the Daily Inventory of Stressful Events (DISE)

## **6 Study Methods**

### **6.1 General Study Design and Plan**

The trial is a randomized, longitudinal, parallel-group, attention-controlled trial. Treatment allocation is a 1:1 ratio. Participants are randomly assigned to LARKSPUR or an emotion-reporting-only attention control condition stratified by race/ethnicity; non-Hispanic Black, Hispanic, or non-Hispanic other (e.g., White, Asian) after completion of eligibility screening

and baseline assessments (see Table 1 for the schedule of trial events). All participants will know their intervention/attention control status.

The LARKSPUR study protocol states that one of the Primary Outcomes is to establish feasibility (Retention as Measured by Change in Enrollment), so Retention will be tested for superiority.

The LARKSPUR study protocol states that the secondary objectives include hypotheses that “intervention participants will report more frequent PA, decreased depressive symptoms, enhanced physical functioning, improved stress appraisals, and reduced FMS pain (intensity and interference) immediately following the intervention (approximately 8 weeks), and at 1-Month Follow-Up.” Therefore, all Secondary Endpoints will be tested for superiority.

Other Primary Outcomes characterize the treatment group only and are not tested statistically.

## **6.2 Inclusion-Exclusion Criteria and General Study Population**

### **6.2.1 Study Population**

Participants 50 years of age or older with a fibromyalgia diagnosis that will be stratified by race/ethnicity; non-Hispanic Black, Hispanic, or non-Hispanic other (e.g., White, Asian).

### **6.2.2 Inclusion Criteria**

**6.2.2.1** Access to daily internet

**6.2.2.2** Male or female 50 years of age or older

**6.2.2.3** Fluent in English and able to read and write in English

**6.2.2.4** Physician diagnosis of FMS AND/OR Score  $\geq 13$  on the 6-item, self-report fibromyalgia screening tool

**6.2.2.5** Report having pain for at least the last three months

### **6.2.3 Exclusion Criteria**

**6.2.3.1** Cognitive impairment

**6.2.3.2** Current behavioral treatment for pain

**6.2.3.3** Enrolled in another pain study

## **6.3 Randomization and Blinding**

Participants are randomized to LARKSPUR or an emotion-reporting-only attention control condition stratified by race; non-Hispanic Black, Hispanic, or non-Hispanic other (e.g., White, Asian).

The random number sequence will be generated and uploaded into REDCap by non-data collecting study staff. Allocation concealment will be utilized to prevent selection bias; group assignment will be given to both the participant and selected study staff only after completion of the baseline assessment.

## 6.4 Study Assessments

**Table 1.** Schedule of trial events

Table 1: Type and Timing of Measures	PS	B	R	DS	PI	M1
Screening						
Age $\geq$ 50, read and understand English, FMS diagnosis, 6-item self-report	•					
FMS screening tool, cognitive functioning, no other behavioral treatment for pain, internet access, race/ethnicity	•					
Demographic and Clinical Characteristics						
Age, race/ethnicity, sex, income, education, employment, marital status		•				
Charlson Comorbidity Index		•				
Pain						
Standardized Pain Measures		•			•	•
Daily report of pain and fatigue				•		
Physical Function						
Body Mass Index (BMI)		•				
PROMIS Physical Function Short Form 10a		•			•	•
PROMIS Fatigue Short Form 6a		•			•	•
Exercise in the last 24 hrs		•		•	•	•
Psychosocial Factors						
Standardized Psychosocial Factor Measures		•			•	•
Daily stressors (DISE)				•		
Daily positive and negative affect				•		
Daily positive events				•		
Feedback and Care Updates						
Feedback Survey					•	
Self-Enrolled Therapy Update						•

PS = pre-study; B = Baseline; R = randomization; DS = daily survey; PI = Post-Intervention; M1 = 1-Month Follow-Up

### 6.4.1 Primary Outcomes

#### 6.4.1.1 Recruitment as Measured by Rates of Enrollment

Enrollment is assessed based on the percentage of participants recruited into the study out of all total eligible participants.

*% Enrollment* = (number of recruited participants meeting eligibility requirements and enrolled into the study) / (number of recruited participants) \* 100.

#### 6.4.1.2 Retention as Measured by Change in Enrollment

Retention is assessed based on the percentage of participants enrolled at Baseline that completed the Post-Intervention assessment.

*% Retention Post-Intervention* = (number of participants enrolled at Baseline that completed the Post-Intervention assessment) / (number of participants enrolled at Baseline) \* 100.

% *Retention 1-Month Follow-Up* = (number of participants enrolled at Baseline that completed the Post-Intervention assessment and 1-Month Follow-Up assessment) / (number of participants enrolled at Baseline that completed the Post-Intervention assessment) \* 100.

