This document is confidential and is to be distributed for review only to investigators, potential investigators, consultants, study staff, and applicable independent ethics committees or institutional review boards. The contents of this document shall not be disclosed to others without written authorization from WCM.

Weill Cornell Medicine

Institution Name

M. [name], PhD

June 29, 2021

Principal Investigator's Name

Principal Investigator's Signature

Date

List of Abbreviations

AE	Adverse Event
CFR	Code of Federal Regulations
COA	Center on Aging
CRF	Case Report Form
CTSC	Clinical Translational Science Center
FDA	Food and Drug Administration
FMS	FibroMyalgia Syndrome
GCP	Good Clinical Practice
HIPAA	Health Insurance Portability and Accountability Act of 1996
ICF	Informed Consent Form
IRB	Institutional Review Board
LARKSPUR	Lessons in Affect Regulation to Keep Stress and Pain UndeR control
NYP	NewYork-Presbyterian
PA	Positive Affect
PHI	Protected Health Information
PI	Principal Investigator
REDCap	Research Electronic Data Capture
WCM	Weill Cornell Medicine

1. Protocol Summary

Full Title:	Positive Affect as a Source of Resilience for Adults in Chronic Pain
Short Title:	LARKSPUR Study
Principal Investigator:	M. [name], PhD (WCM) [name] (Cornell)
Study Description:	Our goal for this study is to evaluate the feasibility, acceptability, and effect size of a previously developed online positive affect (PA) skills intervention—LARKSPUR (Lessons in Affect Regulation to Keep Stress and Pain UndeR control)—in a sample of older adult patients with fibromyalgia syndrome (FMS).
Sample Size:	N= 150
Enrollment:	This study will enroll 150 subjects and screen up to 1,200 subjects
Study Population:	Older adults 50 years of age or older with a physician confirmed diagnosis of FMS, or a self-report physician diagnosis corroborated by a screening measure, that will be stratified by Hispanic, non-Hispanic Black, or non-Hispanic other (e.g., White, Asian).
Enrollment Period:	2 years
Study Design:	This is a longitudinal, randomized behavioral intervention feasibility study with internet trainings, daily reporting, and surveys using REDCap and BrightOutcome for data collection.
Description of Sites/ Facilities Enrolling	
Participants:	We will be enrolling participants only through WCM/NYP and will be recruiting participants through EPIC, physician referral, flyers, letters, social media, and direct recruitment.
Study Duration:	September 30, 2024

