with basic skills for recognizing and savoring positive events and progressing to more complex skills such as goal-setting and acts of kindness.

A week will consist of 1-2 days of didactic material and 5-6 days of real-life skills practice and reporting. Participants cannot skip ahead and can only progress to the next lesson if they have completed the current one, but they can return to old lessons or exercises if they choose. As part of the daily home practice, intervention participants will be asked to complete the daily emotion check-in that comprises the attention control condition (which takes about 5 minutes to complete). Based on past studies, we estimate the time to read through a skill to be about 15 minutes per skill. We also encourage daily interaction with the website (home practice, reporting emotions) and estimate the time involved to be an additional about 10 minutes. Both the LARKSPUR intervention and emotion-reporting attention control conditions, including all home practice and assessments, will be done over the internet from the participant's home, or any other location of their choice. The intervention content, emotion check-in, and are all mobile-enabled so can be completed on desktop, laptop, tablet, or smartphone with web browser access.

Attention Control Condition (n = 75). We sought an attention control condition that provided something to engage participants, but was not expensive or burdensome. In past research we have established that emotion reporting is acceptable as an attention control condition (retention rates of ~80%, similar to or higher than for the intervention), and that participants perceive it as being beneficial, providing some of the features of a placebo control. In this daily emotion-reporting attention control condition, participants will be asked to report how they are feeling daily for 6-8 weeks which will be emailed to control participants.

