**8      General Analysis Considerations****8.1    Analysis Populations****8.1.1    Modified Intention to Treat Population**

All subjects who received any study drug and who participated in at least one post-baseline assessment (i.e., all randomized participants with data following the treatment intervention window).

Participants may be removed from the Modified Intention to Treat Population for analysis if they have (a) no observed data on Post-Intervention assessments, (b) withdrew consent during the study, or (c) were unable to access the online intervention and daily emotion reporting platform.

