### **9.1 Subject Disposition**

[figure not shown]
Enrollment at Baseline and Retention at Post-Intervention and 1-month Follow-Up will be established as described in Section 6.4.

Reasons for participant exclusion during enrollment will include failure to meet inclusion criteria (see Section 6.2), unwillingness to provide informed consent, etc.

Reasons for participant attrition may include withdrawal of consent, disrupted technological access, non-responsiveness during the intervention period on the intervention platform, or failure to complete Post-Intervention or 1-Month Follow-Up assessments.

Participant disposition summary statistics will be produced in accordance with Section 9.

A skeleton CONSORT flow diagram is provided below.

**Table 2.** Study CONSORT flow diagram

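### The SAP's 1-month retention is a stage-to-stage rate not labelled as such, and its enrolment formula does not compute the rate that its own sentence defines

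*SAP*

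**What the plan says.** Recruitment and retention are the first two primary endpoints (SAP 5.2.1).

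**Retention (SAP 6.4.1.2).** The defining sentence reads "Retention is assessed based on the percentage of participants enrolled at Baseline that completed the Post-Intervention assessment". The first formula, for Post-Intervention, uses that Baseline denominator. The second, for 1-Month Follow-Up, is the number who "completed the Post-Intervention assessment and 1-Month Follow-Up assessment) / (number of participants enrolled at Baseline that completed the Post-Intervention assessment". SAP 9.1 refers back to Section 6.4 for these percentages. SAP 8.3 promises retention summaries at each assessment point without giving a denominator. SAP 10.1 compares retention between arms with Boschloo's test and names no time point.

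**Enrolment (SAP 6.4.1.1).** The sentence defines the "percentage of participants recruited into the study out of all total eligible participants". The formula counts those "meeting eligibility requirements and enrolled into the study) / (number of recruited participants". The word 'recruited' is not defined.

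**The concern.** Two rates share the name '% Retention' but have different denominators. The 1-month rate describes only the step from Post-Intervention to 1-month, and neither its name nor the sentence above it says so. It also requires both assessments, so a participant who misses Post-Intervention but returns at 1-month enters neither numerator. The analysis set in SAP 8.1.1 is glossed as "all randomized participants with data following the treatment intervention window", which can include such a person. Item (a) of that section permits their removal but does not require it.

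For enrolment, 'recruited' is the numerator in the sentence and the denominator in the formula. The formula's numerator is restricted to recruited people who meet eligibility, which implies that some recruited people do not. SAP 9.1 points the same way: "Reasons for participant exclusion during enrollment will include failure to meet inclusion criteria". On that reading the formula mixes the share of people who are eligible with the share of eligible people who join.

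Uptake and attrition are what the larger trial must plan on. A planner who takes the 1-month figure as retention from Baseline would usually allow for too little attrition. The enrolment formula would not show what share of eligible people join.

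**Working it through.** The documents give no target or computed enrolment or retention percentage, so there is no figure to reproduce. The check compares each formula with its sentence and shows how far apart they can be.

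**Inputs**
- 75 per arm (Protocol Section 3, Randomization). SAP Section 7 gives 45 per group; the gaps in percentage points do not depend on which is used, apart from rounding to whole participants.
- Past experience with the control condition: "retention rates of ~80%, similar to or higher than for the intervention" (Protocol Section 3, Attention Control Condition). No time point is given; it is taken here as Post-Intervention retention (assumption).
- "This study will enroll 150 subjects and screen up to 1,200 subjects" (Protocol Section 1).
- 1-month completion among Post-Intervention completers: not in the documents; 85–95% assumed.
- Number eligible: not in the documents; 200, 300 or 600 assumed.

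**Retention formulas.** Let p be Post-Intervention retention, c the 1-month completion among Post-Intervention completers, and r the 1-month completion among those who missed Post-Intervention.
- SAP 1-month rate = c
- Share of enrolled completing both = p × c
- Gap = c − p × c = c(1 − p), positive whenever p < 1 and c > 0
- Share of enrolled completing 1-month at all = p × c + (1 − p) × r, which is below c whenever p < 1 and r < c

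**Retention numbers**, with p = 60/75 = 80%:

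| Completed both | SAP 1-month rate | Share of enrolled completing both | Gap (points) |
|---|---|---|---|
| 51 | 51/60 = 85% | 51/75 = 68% | 17 |
| 54 | 54/60 = 90% | 54/75 = 72% | 18 |
| 57 | 57/60 = 95% | 57/75 = 76% | 19 |

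If p is instead assumed to lie between 70% and 90%, the gap runs from 0.85 × 0.10 = 8.5 points to 0.95 × 0.30 = 28.5 points.

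**1-month-only completers**, in the middle row, where 15 of 75 missed Post-Intervention. The SAP figure stays at 90.0% whatever these 15 do.
- None returns: 54/75 = 72.0%
- 13 return: 67/75 = 89.3%
- 14 return: 68/75 = 90.7%
- All 15 return: 69/75 = 92.0%

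The SAP figure is therefore the higher one unless at least 14 of the 15 return.

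**Arm comparison** (hypothetical counts, 45 per arm). On the conditional rate, 27/30 v 36/40 is 90.0% v 90.0%, two-sided Boschloo p = 1.000. The same completers over Baseline, 27/45 v 36/45, are 60.0% v 80.0%, p = 0.045. So the choice of rate can change the test result.

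**Enrolment**, with 150 enrolled:
- Formula, if 'recruited' means everyone screened, at the ceiling of 1,200: 150/1,200 = 12.5%
- Formula, if 'recruited' means the 150 already confirmed eligible and enrolled: 150/150 = 100%
- Sentence: 150/200 = 75%, 150/300 = 50% or 150/600 = 25%

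Neither reading of the formula gives the sentence's quantity.

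**The case against.** The strongest defence is that the 1-month rate is a disclosed choice. Its full numerator and denominator are printed, and the defining sentence speaks only of Post-Intervention, so the second formula contradicts no stated 1-month definition. SAP Section 7 is itself concerned with attrition between end of trial and follow-up, which is what a conditional rate measures. SAP 9.1 lists failure to complete either later assessment among the reasons for attrition, so someone who missed Post-Intervention may already count as lost. The two rates multiply to give completers of both, and attrition summaries and a CONSORT flow are planned.

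Much of this is fair, and it limits the harm: the share completing both is recoverable, and the gap separates two quantities rather than biasing an estimate. It does not remove the problem. A primary endpoint should not need back-calculation to mean what its name suggests, SAP 9.1 sends the disposition percentages back to the same formulas, and no product of the two rates recovers 1-month-only completers. Whether there will be any is not known from the documents, and the flow diagram, which is not shown, may count them.

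On enrolment, the 12.5% is fragile. It uses the screening ceiling, and Protocol 4.4 uses 'recruited' for patients already confirmed eligible. That usage does not rescue the formula, since it drives the result towards 100%. It strengthens the case for defining the term.

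**Conclusion.** The concern holds and should be fixed. The enrolment sentence and formula define different quantities for a primary endpoint. The 1-month retention rate is conditional without being named so, and omits 1-month-only completers.

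The 1-month rate exceeds the share of enrolled completing both by 17 to 19 points at 80% Post-Intervention retention and 85–95% conditional completion, and by 8.5 to 28.5 points if Post-Intervention retention is 70–90%. These stage rates are assumptions, apart from the roughly 80% past retention, whose time point is assumed. That the SAP figure will usually be the more favourable one rests on those who missed Post-Intervention being less likely to complete 1-month than those who did not. The size of the enrolment discrepancy cannot be fixed from the documents, because 'recruited' and the number eligible are not given.

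The Post-Intervention rate is correctly defined. The missing time point for Boschloo's test needs clarification only, since the sentence in SAP 6.4.1.2 points to Post-Intervention. No progression threshold is stated, so the effect is on reported feasibility and the planning of the larger trial. No treatment-effect estimate is affected.

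**What to change.** 1. In SAP 6.4.1.2, define 1-month retention as participants completing the 1-month assessment, whether or not they completed Post-Intervention, divided by all enrolled at Baseline.
2. State that for the between-arm comparison the denominator is all randomised to the arm. Randomisation follows the baseline assessment (Protocol Section 3; SAP 6.3), so enrolled and randomised counts can differ; report anyone enrolled but not randomised.
3. Keep the present 1-month rate as a supplement, labelled as conditional on completing Post-Intervention.
4. In SAP 6.4.1.1, make the formula enrolled over eligible, define 'recruited', and report eligible over screened separately.
5. In SAP 10.1, confirm that Boschloo's test uses Post-Intervention retention with the all-randomised denominator.

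The cost is SAP wording and minor programming, with no new data. The 1-month retention figure will usually look less favourable.

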#### **6.4.1.3 Helpfulness, Satisfaction, and Impact as Assessed by Self-Report Participant Feedback Survey**

##### **6.4.1.3.1 Rating of Recommending Intervention to Friend**

The item is measured on an 11-point Likert scale for which 0=Definitely Not to 10=Definitely Yes. Assessed at Post-Intervention.

##### **6.4.1.3.2 Rating of Recommending Intervention to Those with Chronic Pain**

The item is measured on an 11-point Likert scale for which 0=Definitely Not to 10=Definitely Yes. Assessed at Post-Intervention.

#### **6.4.1.4 Length of Intervention Time as Measured by Number of Weeks to Complete the Intervention**

Length of Intervention Time is assessed based on the number of weeks from the time participants first accessed the online intervention platform to the time participants completed all unique weekly home practice exercises at least once. Assessed at Post-Intervention.

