1.1.2 Hypotheses / Research Questions

We hypothesize that the intervention will lead to more frequent daily PA, which, in addition to directly affecting depressive symptoms, will also have indirect effects through enhanced physical functioning and improved stress appraisals (*resilience mechanisms*). Decreased depressive symptoms, enhanced physical functioning, and improved stress appraisals, in turn, are hypothesized to lead to reduced FMS pain (*resilience outcomes*).

2. Background and Significance

Chronic non-cancer pain affects as many as 100 million Americans and is associated with significant functional limitations and physical disability. Standard behavioral therapies typically focus on minimizing negative thoughts and emotions associated with pain and yield only modest treatment effects. Efforts are therefore needed to develop more effective psychological treatments for chronic pain by identifying new targets for intervention. We propose to pilot test a resilience-based intervention that targets positive affect (PA) in fibromyalgia syndrome (FMS) patients, a chronic pain population with known deficits in PA and an inability to regulate PA in the face of pain. Our goal is to conduct a randomized pilot trial of LARKSPUR (Lessons in Affect Regulation to Keep Stress and Pain UndeR control), an online-delivered PA skills intervention. Our central hypothesis is that our LARKSPUR program will (a) show acceptability and feasibility in engaging and retaining FMS patients and (b) demonstrate greater improvements in PA and FMS-related pain and functional impairment.

This proposal for pilot data collection will lay the foundation for a high-quality randomized trial for people with FMS. The proposed work holds promise as an effective, low cost, scalable, and readily implementable novel non-pharmacologic intervention to help people cope with FMS. By demonstrating the feasibility, acceptability, and preliminary efficacy of the LARKSPUR intervention, we hope to improve quality of life, as well as the options available for care for millions of people who suffer from FMS.

3. Study Design and Methods

The LARKSPUR online intervention will be hosted and maintained by a HIPAA compliant application developer (BrightOutcome) via a web-based platform. The order of the skills has been finalized and skills are unlocked by week as follows:

- Week 1: Noticing and Savoring Positive Events
- Week 2: Strengths and Activation
- Week 3: Mindfulness

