- Week 4: Positive Reappraisal and Gratitude
- Week 5: Acts of Kindness
- Week 6: Wrap-Up

The following table is the LARKSPUR intervention content.

Table 1. Intervention Content

Week 1	Noticing and Savoring Positive Events	Recognizing cognitive biases that can lead to discounting or failing to remember positive events. Skills for scheduling pleasant events according to level of pain
	Exercises	Daily positive events journal
Week 2	Strengths and Activation	Support for acknowledging strengths even in the presence of pain-related limitations. Emphasis on setting small, attainable goals and working up to challenging goals gradually. How to select goals that will provide pleasure or mastery experiences.
	Exercises	Daily strengths journal (record ways a personal strength or talent was used) Activity journal
Week 3	Mindfulness	Using present-focused awareness to combat rumination about chronicity of pain and pain-related limitations Using acceptance to tolerate unpleasant situations with less negative emotion
	Exercises	Select an everyday activity to do mindfully Mindful breathing recorded meditation (10 minutes)
Week 4	Positive Reappraisal and Gratitude	Role of negative cognitions in causing or maintaining stress and contributing to pain
	Exercises	Daily reappraisal journal Daily gratitude journal
Week 5	Acts of Kindness	Include benefits of compassion toward self and others (e.g., decreased stress and pain; improved relationships) Small prosocial acts that can be performed even if one is relatively socially isolated or has limited mobility
	Exercises	Do something nice for someone else each day and record it in a daily kindness journal
Week 6	Wrap-Up	Review the LARKSPUR course, reflect on skills learned, and make a plan for continued practice.

Randomization. Once participants complete consent and baseline questionnaire, participants will be randomized 1:1 to LARKSPUR (n = 75) or an emotion reporting only attention control condition (n = 75) stratified by race/ethnicity. The random number sequence will be generated and uploaded into REDCap by a non-data collecting co-investigator under the guidance of the study statistician and REDCap/CTSC personnel. All participants will know their intervention/attention control status.

LARKSPUR intervention (n = 75). The LARKSPUR intervention will be based on our current online positive affect intervention which consists of skills for increasing the frequency of positive emotions, beginning

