### 10.1 Primary Efficacy Analysis

The Recruitment Primary Outcome will be calculated as described in Section 6.4.

The Retention Primary Outcome treatment group percentages will be compared using Boschloo's Test at the 2-sided 5% significance level under the null hypothesis that retention rates are equal between treatment groups [15]. The maximum likelihood estimate of the odds ratio of treatment retention to control retention will be computed with a 2-sided 95% confidence interval and p-value.

The Rating of Recommending Intervention to Friend and Rating of Recommending Intervention to Those with Chronic Pain items will be summarized using an ordinal regression (proportional odds) model without predictors (i.e., the ordinal properties of the Likert scales of these two items will be respected by estimating the average rating adjusted for the cumulative category response probability distribution) [16]. The modified Intention-to-Treat sample described in Section 8.1 will be used.

The Length of Intervention Time will be calculated as described in Section 6.4.

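### Length of Intervention Time has no value for participants who do not finish, and its stop rule can be met before the Week 6 session, so the planned summary describes finishers only and tends to understate the time needed

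*SAP*

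**What the plan says.** SAP 5.2.1 lists the number of weeks to complete the intervention as one of four primary endpoints. SAP 6.4.1.4 starts the clock when a participant first uses the platform and runs it "to the time participants completed all unique weekly home practice exercises at least once". The analysis section, SAP 10.1, adds only this: "The Length of Intervention Time will be calculated as described in Section 6.4". It names the modified intention-to-treat set for the two recommendation ratings but no analysis set for this endpoint. SAP 6.1 says that primary outcomes other than retention describe the treatment group and are not tested.

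SAP 9 plans descriptive statistics, including the non-missing sample size, for weeks to complete and for sessions completed. Its tables are to carry the total population, missing observations included.

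Protocol Section 3 describes the course. Its "skills are unlocked by week as follows", over six weeks, and participants "can only progress to the next lesson if they have completed the current one", although they may go back to earlier material. Table 1 there has an exercises row for each of Weeks 1 to 5. The last is Week 5: "Do something nice for someone else each day and record it in a daily kindness journal". Week 6 (Wrap-Up) has a description, "Review the LARKSPUR course, reflect on skills learned, and make a plan for continued practice", but no exercises row. The intervention period is given as 6-8 weeks.

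**The concern.** The definition needs an event, namely the last outstanding exercise being done. Someone who stalls never has that event, and someone who never logs in has no start time either. The SAP expects such people: SAP 9.1 counts loss of technical access and silence on the platform among the reasons for attrition. If they simply have no value, the reported mean and median describe only those who got through.

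The stop rule also rests on exercises, and the last one listed belongs to Week 5. A participant could be recorded as having completed the intervention without opening its final session.

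At stake is what the pilot tells the next trial. SAP 7 says the study's main purpose is to assess the feasibility of methods and procedures for a larger trial. The figure for how long the course takes should not depend on leaving out those for whom it took too long.

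**Working it through.** The documents give no target, completion rate or expected duration for this endpoint, so there is no stated figure to reproduce.

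**1. Who has a value.** SAP 6.4.1.4 requires every unique exercise to be done at least once, so one exercise never done leaves the time undefined. SAP 10.1 adds no rule. The general missing-data rule in SAP 8.3 is a mixed model with participant random intercepts. That suits repeated outcome scores; it cannot supply the time of a one-off event that did not occur. The result is a finishers-only summary.

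**2. When the clock can stop.** Assume weekly unlocking counted from first access. Week *k* then opens on day 7 × (*k* − 1), so Week 5 opens on day 28 and Week 6 on day 35. Protocol Section 3 gives 1-2 didactic days per week; 0 is added as the extreme case.

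- One Week 5 entry after 0, 1 or 2 didactic days: 28/7 = 4.00, 29/7 = 4.14 or 30/7 = 4.29 weeks.
- Latest on-schedule stop, at the end of Week 5: 35/7 = 5.0 weeks.
- End of the six-week course: 42/7 = 6.0 weeks.

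For an on-schedule participant the recorded time is therefore 6.0 − 5.0 = 1.0 to 6.0 − 4.0 = 2.0 weeks shorter than the course.

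**3. How many would have no value.** The LARKSPUR arm is 75 in Protocol Section 3 and 45 in SAP 7, so both are shown. Completion of 50-90% is an assumption. Counts are rounded to whole participants.

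| Completion | No value, of 45 | No value, of 75 |
|---|---|---|
| 90% | 5 | 7 |
| 80% | 9 | 15 |
| 70% | 14 | 23 |
| 60% | 18 | 30 |
| 50% | 23 | 37 |

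**4. Size of the shift in the mean.** Assume a finisher mean of 6.0 weeks and set non-finishers at 8 weeks. With completion *p*, the mean over everyone is *p* × 6.0 + (1 − *p*) × 8.0:

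- 80%: 4.8 + 1.6 = 6.4 weeks
- 60%: 3.6 + 3.2 = 6.8 weeks
- 40%: 2.4 + 4.8 = 7.2 weeks

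The finishers-only mean is 6.0 weeks in each case.

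**5. The same check on the median.** Assume instead that finishers' times are uniform from 29/7 = 4.14 to 8 weeks. Their median is (4.14 + 8)/2 = 6.07 weeks. If non-finishers count as not complete at 8 weeks, the median over everyone is the 0.5/*p* quantile of finishers, 4.14 + 3.86 × 0.5/*p*. This gives 6.29, 6.55, 6.90, 7.36 and 8.0 weeks at 90%, 80%, 70%, 60% and 50% completion.

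**6. Precision of a completion percentage.** At an assumed 80%, Wilson 95% intervals are 66.2-89.1% for 36/45 and 69.6-87.5% for 60/75.

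**The case against.** The strongest reply is that SAP 9 already calls for the non-missing count and the total population, so non-finishers are not wholly hidden and a completion share could be derived. That stands, and it rules out saying that the trial cannot show whether the course is completed. What remains is narrower. No completion percentage, interval or 6- or 8-week cut is defined. Which total applies is not stated. Sessions completed is also a different event from all exercises done.

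Three stronger readings are tempting, but the documents do not support them.

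- *The stop rule is always met before Week 6.* It can be, but need not be. Participants may go back to earlier exercises, and no section says that finishing a lesson requires doing its exercises. Someone could reach Wrap-Up with a journal outstanding and stop the clock later. Table 1 may also not list everything on the platform.
- *Values must lie between about 4 and 8 weeks.* No section closes access at 8 weeks or says that unlocking is timed from first access.
- *The more people fail to finish, the faster the result looks.* The illustrations hold finishers' times fixed, so they show a gap from the all-participant figure, not a falling finishers' figure.

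It is also fair that the endpoint is descriptive. No test, error rate or go/no-go threshold depends on it, and time among completers is a legitimate quantity if labelled as such.

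**Conclusion.** The point holds in limited form. As written, the endpoint is undefined for anyone who does not do every exercise, and no denominator or rule covers them. The reported time therefore describes finishers, tends to understate the time needed, and does not alone give the proportion completing in the 6-8 week period. Separately, if Table 1 is the full exercise list, the rule can be met at about 4.0-5.0 weeks by an on-schedule participant who has not opened Wrap-Up.

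The gap over reading from the documents alone is certain in kind but not in size. Under the assumptions in the working, the mean moves from 6.0 to 6.4 weeks at 80% completion and to 7.2 at 40%. With few non-finishers it would be small. The calendar figures rest on weekly unlocking from first access. This is an improvement worth making to a primary feasibility endpoint; it does not invalidate the trial.

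**What to change.** **SAP 6.4.1.4.** Define completion as all Week 1-5 exercises done at least once plus the Week 6 Wrap-Up completed, or state why Wrap-Up is not counted.

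**SAP 10.1.**

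- Report the number and percentage of all participants randomised to LARKSPUR who complete by 6 and by 8 weeks, with 95% confidence intervals. Count non-finishers and those who never log in as not complete.
- Give the median time with non-finishers treated as not complete at 8 weeks (Kaplan-Meier, if the median is reached). When all non-finishers are carried to 8 weeks, this agrees with the simple proportions.
- Keep the finishers' time, still measured from first access, as a descriptive line labelled 'among completers'. Nothing here requires moving the start of the clock to randomisation, which would be a different quantity.

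**Cost.** A few sentences and one short table. Protocol Section 3 says that log-ins, exercises done and skills done are already stored, so the extra work is mainly analysis of existing log data; the sponsor should check that Wrap-Up completion is logged. The reported figure will look less favourable.
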